## 9. Efficacy Evaluation

### 9.1 Definition

#### 9.1.1 General Definition

Evaluable toxicity: All patients who have received at least 1 month of TPM treatment are evaluable for toxicity evaluation from the first treatment.

Evaluable objective response: Only patients who have a measurable disease at baseline, have received at least 1 treatment cycle, and have been re-evaluated for the disease will be considered as evaluable responses. These patients will be categorized for their responses according to the following definitions (Note: Patients who demonstrate objective PD or death by the end of Cycle 1 will also be considered evaluable).

## 9.2 Efficacy Evaluation

The evaluation will be started from Month 3. Hematologic ORR is defined as the sum of CR and PR.

Hematologic CR: Clinical symptoms and signs turn normal (splenomegaly disappears), and blood cell count completed turn normal, ie, hemoglobin >110 g/L, platelets >100 ×  $10^9$ /L, ANC >1.5 ×  $10^9$ /L, lymphocyte count <4 ×  $10^9$ /L, and LGLs in peripheral blood are within the normal range (<0.5 ×  $10^9$ /L).

Complete molecular response: No LGLs can be detected when reaching CR (negative TCR rearrangement by flow cytometry or polymerase chain reaction [PCR]).

Hematologic PR: Hematologic PR is defined as blood cell count that do not meet criteria for CR but improvement is observed, such as neutrophil counts  $>0.5 \times 10^9/L$  without repeated infection, an increase of hemoglobin level from baseline by more than 20 g/L without blood transfusion, platelets  $>50 \times 10^9/L$ .

SD: CR/PR criteria are not met after standardized treatment for 4 months, but no significant progression is observed.

PD: Worsening of hematologic parameters in patients previously achieving PR/CR.

PFS: PFS is defined as the time from the first day of study to PD or death, including PD and death from any cause (eg, PD, toxicity, unrecorded progression in a new treatment, or death).

DoR: DoR is defined as the time when CR or PR is met until the first date of recurrent or progressive disease.

TTNT: TTNT is defined as the time between the start of TPM regimen and the start of the subsequent treatment line.

## 9.3 Study Endpoints Definition and Evaluation

## **Primary Endpoint:**

• CRR of patients with symptomatic LGLL treated with thalidomide, prednisone, and methotrexate.

## **Secondary Endpoints**

## 1. Secondary Safety Endpoint

Incidence and severity of hematological and non-hematological AEs

Safety endpoints include SAEs, treatment-emergent adverse events (TEAEs), physical examination (including ECOG performance status), vital sign measurements, standard clinical laboratory parameters, and ECG. TEAEs will be graded according to NCI CTCAE Version 5.0.

## 2. Secondary Efficacy Endpoints

• Response rates: ORR and PR rate (time frame: 24 months after the last treatment)

Point estimates of rates will be calculated for each protocol analysis set. An estimate of the 95% CI for the response rate will also be derived. Graphical and descriptive analyses will be used to explore associations between relevant markers and responses.

PFS and OS (time frame: 24 months after the last treatment)

Time from the first day to PD or death from any reason. The median duration of the overall response will be assessed with a 95% CI.

• DoR (time frame: 24 months after the last treatment)

The time when CR or PR is met until the first date of recurrent or progressive disease. The median duration of the overall response will be assessed with a 95% CI.

- TTNT (time frame: 24 months after the last treatment)
- Effect of biomarkers on efficacy and adverse reactions

## **Exploratory Endpoint:**

• To explore biomarkers significantly and potentially associated with clinical efficacy

## 10. Safety Evaluation

Timely, accurate, and complete reporting and analysis of safety information from clinical studies are essential to protect patients and investigators and are mandatory by regulatory authorities worldwide. Each AE verbatim term will be coded to a system organ class and preferred term using the Medical Dictionary for Regulatory Activities (MedDRA).

## 10.1 Definition and Classification of Adverse Events

#### **Adverse Events:**

An AE is any untoward medical occurrence in a patient to whom a medicinal product is administered, and which does not necessarily have a causal relationship with this treatment. An AE can therefore be any unfavorable and unintended sign (eg, an abnormal laboratory finding), symptom, or disease temporally associated with the use of a medicinal product, whether considered related to this medicinal product. (As defined by the International Council for Harmonisation of Technical Requirements for Pharmaceuticals for Human Use [ICH]).

It includes any new event, any event worsened from baseline in severity or frequency, or abnormal results of diagnostic procedures, including laboratory test abnormalities.

#### **Serious Adverse Events:**

An SAE, as defined by ICH, as an AE that fulfils one or more of the following criteria at any dose:

- Results in death
- Is life-threatening ((life-threatening refers to a reaction in which the patient was at risk of death at the time of the reaction; it does not refer to a reaction that hypothetically might have caused death if more severe).)
- Requires hospitalization or prolongation of existing hospitalization
- Results in persistent disability/incapacity (The term disability means a substantial disruption of a person's ability to conduct normal life functions.)
- Is a congenital anomaly/birth defect
- Is an important medical event

Note: Medical or scientific judgment should be exercised in deciding whether SAE reporting is appropriate in other situations such as important medical events that may not be immediately life-threatening or result in death or hospitalization but may jeopardize the patient or may require medical or surgical intervention to prevent one of the other outcomes listed in the above definition. These events should usually be considered serious.

Events that are not considered SAEs include planned hospitalization before enrollment

into the clinical study; a disease for elective treatment and unrelated to the indication under study or its treatment; events occurring in an emergency outpatient department and not leading to hospitalization (unless other criteria above are met); part of normal treatment or monitoring of the study indication and unrelated to condition worsening.

If an AE is considered serious, the AE page in the CRF and the SAE Report Form must be completed. The investigator will provide information on severity, start and end dates, relationship to the study drug, actions taken with the study drug, and outcomes.

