#### 2.6.2 Potential Risks

According to the preliminary summarized clinical safety data, the adverse reactions of thalidomide combined with immunosuppressants and hormones regimen were mainly gastrointestinal reactions and peripheral neuropathy, manifested as numbness of hands and feet, loss of appetite, constipation, dizziness, etc. However, the adverse reactions were mainly Grade 1 or 2 and could be managed. The most severe toxicities of thalidomide were embryo-fetal toxicity and venous thromboembolism. Due to the risk

of embryo-fetal toxicity and venous thrombosis. Pregnant and lactating women will be excluded from the study and those who become pregnant during the study will be promptly withdrawn from the study. Due to the risk of venous thromboembolism, high-risk patients based on the Caprini score for venous thromboembolism will be excluded from this study. Patients will take aspirin concurrently with oral thalidomide to prevent venous thromboembolism and coagulation function will be monitored at the end of each cycle. The preliminary data of this study showed that except for 1 Grade 3 nausea, no other Grade  $\geq$ 3 adverse reactions occurred and all adverse reactions were clinically manageable. The safety of thalidomide combined with methotrexate and prednisone will be monitored in this study.

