## 4.8 Study Termination

EOS is defined as the last patient last visit at the end of the follow-up period, which will be the last data collection point and the last patient may be an outpatient or laboratory sample. EOS is expected to occur approximately 2 years after enrollment of the last patient. A patient will be considered to have completed the study if he/she dies or meets any of the withdrawal criteria.

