## 8.5.2 Safety Follow-up

Safety follow-up will be performed for all patients who complete or discontinue treatment until 1 year after the last dose of the study drug, or until initiation of a new antineoplastic therapy (whichever occurs first).

Patients will be contacted by phone 1 year after the last dose, or asked to the study site for a safety visit to collect the ongoing AEs or changes in laboratory abnormalities, and to assess new AEs, SAEs, new concomitant medications, or changes in current medications since the last assessment. Any new conditions that occur during the safety follow-up need to be documented in the CRF as appropriate. After the safety follow-up (ie, 28 days after the last dose), there is no need to actively collect AEs. However, if an SAE occurs and the investigator assesses a reasonable causality to the study drug, the SAE should be reported.

AEs (regardless of causality) that do not completely resolve at the end of safety followup must be followed up until recovery (chronic, baseline value, or completely recovery), or clinical stability is achieved.

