# **10.2** Safety Evaluation

If a patient completes at least 1 month of effective treatment, the patient will be analyzed for safety. The tolerability of treatment will be assessed by evaluating laboratory parameters and AEs. The incidence of all AEs during the treatment and up to 30 days after the last drug administration will be recorded.

AEs will be classified by severity, duration, and frequency. Details of AEs will be listed by patients, including time of onset, duration, toxicity grade, corrective treatment, outcome, and relationship to the investigational product. Safety parameters will be assessed by 2 independent investigators who will assess severity and treatment each time.

Study drug should be discontinued for any uncontrolled non-hematological toxicity that may be associated with the study drug and of Grade 3 or higher, and for any hematological toxicity that meets the criteria. For patients requiring full-dose anticoagulation (eg, heparin), the study drug should be interrupted until the anticoagulation is stable. For patients requiring an invasive procedure or surgery, the study drug must be interrupted. Any other clinically important events, in which the investigator may deem appropriate dose delays, must be discussed with the CRA. Details of drug adjustment and discontinuation criteria, refer to Section 7.4.

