# 10.4 Reporting of Adverse Events

All AEs and SAEs that occur between the first study-related procedures and within 30 days after the last dose of the study drug will be reported. All AEs, regardless of severity or presumed relationship to the study drug, must be recorded on the CRF using medical terms.

Refer to

(https://ctep.cancer.gov/protocolDevelopment/electronic\_applications/docs/CTCAE\_v 5\_Quick\_Reference\_5x7.pdf) for details. The investigators also need to record their opinions on the relationship between AEs and the study drug on the CRF. All actions required for AE management must be recorded in the source documents. All SAE reports must be submitted within 24 hours. For initial SAEs, all case details should be collected within 24 hours. The initial report must be as complete as possible, including details of the current diseases and SAEs, as well as an assessment of the causality between the event and the study drug. Information that is not available at the time of initial reporting (eg, end date or laboratory values of AEs) must be recorded on subsequent SAE forms when available and/or immediately upon request. The investigator must keep a copy of all SAE information on file. All SAEs that are unresolved at the time a patient discontinues study must be followed until the event is fully resolved, stabilized/sequelae resolved, or baseline (if any) is returned.

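### Version 2.0 counts a birth defect as an SAE but has no rule for reporting a pregnancy or following it to its outcome, and its 28-day, 30-day and 1-year safety limits conflict

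*Supplement*

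**What the plan says.** All references are to protocol version 2.0.

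- **SAE definition (10.1).** The listed criteria include "Is a congenital anomaly/birth defect".
- **Pregnancy and study status.** Pregnancy is item 7 of the withdrawal criteria in 5.3. Section 2.6.2 states that "those who become pregnant during the study will be promptly withdrawn from the study". Section 4.8 adds: "A patient will be considered to have completed the study if he/she dies or meets any of the withdrawal criteria".
- **30-day limit.** Section 10.4 covers "All AEs and SAEs that occur between the first study-related procedures and within 30 days after the last dose of the study drug". Section 10.2 agrees: AEs during treatment and "up to 30 days after the last drug administration will be recorded".
- **1-year and 28-day limits (8.5.2).** Safety follow-up applies to everyone who finishes or stops treatment and lasts "until 1 year after the last dose of the study drug, or until initiation of a new antineoplastic therapy", with a contact at 1 year to assess new AEs and SAEs. The same section then places the end of safety follow-up at 28 days after the last dose, after which "there is no need to actively collect AEs". An SAE that the investigator considers reasonably related to study drug should still be reported later, and no end date is set.
- **Other contacts.** Section 8.4 has a visit three months after the last treatment that includes AE assessment, then contact twice a year until end of study. Section 8.5.1 re-examines patients every 6 months for 2 years. Section 5.4 asks for safety follow-up to be completed after discontinuation.
- **Notification.** Under 5.3 the investigator tells the Principal Investigator of a discontinuation for any listed reason and records the date and reason on the CRF.

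No section makes a pregnancy a reportable event or sets out follow-up of an exposed pregnancy to its outcome.

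**The concern.** An SAE criterion works only if something leads the site to learn of the event. For a congenital anomaly that means knowing of the pregnancy and staying in contact until it ends. Here the pregnancy is what takes the patient out of the study, and two of the three stated limits close long before a birth.

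The protocol itself makes this matter. Section 7.1 calls thalidomide a highly potent human teratogen, even after a single dose, and cites about 40% mortality at or shortly after birth among exposed infants. Section 2.6.2 names embryo-fetal toxicity among the drug's most severe toxicities. If a site follows the shorter limits, which it may do and still comply with the text, the outcome of such an exposure may never reach the safety data. An absence of reported birth defects would then say little about whether one occurred.

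**Working it through.** The plan gives no figure to reproduce. The check compares the timing of a birth with each stated limit, then asks what would trigger collection.

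**Step 1: time from last dose to birth.** The documents give no gestation length or detection delay, so both are assumptions: conception to birth G = 238 to 280 days (term about 266), and last dose d = 0 to 84 days after conception.

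Days from last dose to birth = G − d.

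- Shortest: 238 − 84 = 154 days.
- Longest: 280 − 0 = 280 days.
- At term: 266 − 84 = 182 to 266 − 0 = 266 days.

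This is roughly 5 to 9 months.

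**Step 2: against the three limits.**

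| Limit | Section | Birth at 154 to 280 days |
|---|---|---|
| 28 days | 8.5.2 (stated end of safety follow-up) | outside by 126 to 252 days |
| 30 days | 10.2, 10.4 | outside by 124 to 250 days |
| 1 year (365 days) | 8.5.2 (stated duration) | inside, with 85 to 211 days to spare |

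The answer depends entirely on which limit a site applies. An early loss could fall inside 30 days. A pregnancy ending 154 days after conception would end 154 − 84 = 70 to 154 − 0 = 154 days after the last dose, again outside both short limits.

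**Step 3: what triggers collection after 28 or 30 days.**

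- The rules in 5.3, 8.5.2 and 10.4 for following unresolved events apply to AEs or SAEs. Section 10.1 defines an AE as an untoward occurrence in a patient given the product. A pregnancy is not plainly one, and an infant is not that patient, so an ongoing pregnancy does not clearly start any of these rules.
- The three-month visit in 8.4 precedes every birth in the assumed range. The later contacts there concern survival, disease status and long-term toxicity; pregnancy is not mentioned. They run only to end of study, which 4.8 expects about 2 years after the last enrolment, while thalidomide alone may run 2 years (6.1).
- The 1-year follow-up ends early if a new antineoplastic therapy begins.
- The open-ended clause for late SAEs requires the investigator to hear of the birth and judge it related.
- Section 5.3 lists withdrawal criteria but goes on to speak of treatment discontinuation, while 4.8 treats meeting a criterion as study completion. It is therefore unclear whether the follow-up for patients who discontinue treatment applies to a patient withdrawn for pregnancy.

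**Step 4: how many patients.** Section 2.1 puts 10% of T-LGLL patients under 40 and reports no gender difference. Applying that to the 42 planned patients and assuming half are women: 42 × 0.10 × 0.5 = 2.1, about 2 women. This leaves out women aged 40 or over who could conceive and the partners of male patients. Women of childbearing potential not using contraception are excluded (5.2.2), so few pregnancies are expected.

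**The case against.** The strongest reply is that the protocol already has several routes to the outcome. The 1-year follow-up in 8.5.2 covers everyone who discontinues, includes a contact for new SAEs, and contains every birth in the assumed range. A related SAE remains reportable after that without limit, and with a drug the protocol calls a potent teratogen, causality is a low hurdle. Sections 5.4, 8.4 and 8.5.1 provide further contacts. Under 5.3 the Principal Investigator is told of the withdrawal and its reason, and the monitoring committee reviews dropout and accumulated safety data (4.7).

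This defeats some stronger readings a reader might draw: that the birth-defect criterion cannot operate, that the 1-year call is the only later contact, that any affected birth would be missed, or that the monitoring committee would not learn of the exposure. The documents support none of these.

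It does not close the gap. The 1-year route stands beside a 28-day statement in the same section and a 30-day rule in two others, and nothing says which prevails. The remaining routes do not tell anyone to ask about the pregnancy. Notifying a withdrawal reason records that the pregnancy occurred, not how it ended, and 5.3 sets no timeline for doing so.

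**Conclusion.** The point holds in a limited form. Version 2.0 names a birth defect as an SAE but provides no procedure for reporting a pregnancy or learning its outcome, and its 28-day, 30-day and 1-year limits contradict one another. Under either short limit a birth, about 5 to 9 months after the last dose, is not actively collected. It is captured only if the 1-year reading is applied and not cut short by new therapy, if a later visit happens to reveal it, or if the investigator hears of it and judges it related.

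The timing rests on assumed gestation and exposure ranges, but the conclusion for the short limits is not sensitive to them: the earliest birth is still 124 days beyond the 30-day limit. The expected number of pregnancies is small, and the primary endpoint is unaffected. The change is worth making because the hazard the protocol describes is severe and the cost is low.

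**What to change.** This concerns reporting only; no treatment rule needs to change.

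- **8.5.2, 10.2, 10.4:** reconcile the 28-day, 30-day and 1-year limits, so that each section states the same period for active AE and SAE collection.
- **10.4:** make any pregnancy arising during treatment or the AE window reportable on the existing 24-hour SAE timeline.
- **4.8, 5.3, 8.5.2:** state that withdrawal for pregnancy does not end safety follow-up, which continues until the pregnancy outcome is known, including after a new antineoplastic therapy starts. The existing rule in 5.4 for patients who withdraw consent to contact would still apply.
- **10.1 or 10.4:** state that any congenital anomaly after exposure is reported as an SAE whatever its date.

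The cost is a short amendment, a pregnancy report form, and a few extra contacts for what is likely to be very few patients.

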## **Suspected Unexpected Serious Adverse Reaction:**

For unexpected AEs, their nature or severity is inconsistent with the that of the study drug. For the study drug, the expectedness of an AE will depend on whether it is listed in the Investigator's Brochure of the study drug. For a drug with marketing authorization, the expectedness of an AE will depend on whether it is listed in the summary of product characteristics (SmPC).

#### **Severity Assessment:**

For AEs and SAEs, the investigator must assess the severity of the events. According to the NCI CTCAE Version 4.03, the severity of AEs will be graded from 1 to 5. A copy of the NCI CTCAE Version 5.0 can be downloaded from the homepage of the Cancer Therapy Evaluation Program (CTEP) (https://ctep.cancer.gov/protocolDevelopment/electronic\_applications/docs/CTCAE\_v 5\_Quick\_Reference\_5x7.pdf). In those cases where NCI CTCAE is not applicable, the severity should be defined according to the following criteria:

#### Grade Definition:

Grade 1 (mild AE): asymptomatic or mild symptoms; usually transient, not requiring treatment, and generally not interfering with daily activities

Grade 2 (moderate AE): Moderate discomfort, interfering with daily activities; usually relieved by basic treatment

Grade 3 (severe AE): Severe incapacitation, inability to perform daily activities, or significantly affecting clinical status, requiring intervention. Hospitalization may or may not be required.

Grade 4 (life-threatening or disabling AE): Life-threatening consequences, life-threatening; requiring hospitalization and clinical intervention.

Grade 5 (AE-related death): Death related to AE

### **Causality Assessment:**

The investigator must determine that the relationship between the administration of the study drug and AEs/SAEs as defined below:

• Unrelated. AEs are not related to the use of the study drug.

- Unlikely/suspicious. AEs that are more likely to have alternative explanations, such as concomitant medications, concomitant diseases, or temporal relationships suggest little causality.
- Possibly. Treatment with the study drug caused or contributed to the AE.
   Alternative explanations, such as concomitant medications and diseases, are uncertain. The event follows a reasonable temporal sequence from the time of drug administration; therefore, causality cannot be ruled out.
- Probably. AEs are probably caused by the use of the study drug. A reasonable temporal sequence of the event with drug administration exists Alternative explanations don't make sense, such as concomitant medications and concomitant diseases.
- Definitely. AEs that are listed as possible AE reactions and cannot be reasonably
  explained by alternative explanations, such as concomitant medications and
  concomitant diseases. The relationship in time is very suggestive (eg, it is
  challenged and re-challenged).
- Non-evaluable: The evidence for making a clinical judgment of causality is insufficient or incomplete.

